2. LIST OF ABBREVIATIONS

ACR	Albumin to creatinine ratio
ALP	Alkaline phosphatase
ALT	Alanine transaminase
APTT	Activated partial thromboplastin time
ASD	Absolute standardized differences
AST	Aspartate transaminase
BMI	Body mass index
BP	Blood pressure
CCI	Charlson comorbidity index
CI	Confidence interval
COPD	Chronic obstructive pulmonary disease
DCCO	Diffusing capacity of carbon monoxide
EMR	Electronic medical records
ER	Emergency room
FEV1	Forced expiratory volume in one second
FVC	Forced vital capacity
GERD	Gastroesophageal reflux disease
GFR	Glomerular filtration rate
GGT	Gamma-glutamyl transpeptidase
HDL	High-density lipoprotein
HIPPA	Health Insurance Portability and Accountability Act
HRCT	High resolution computed tomography
ICD-9-CM	The International Classification of Diseases, Ninth Revision, Clinical Modification
ICD-10-CM	The International Classification of Diseases, Tenth Revision, Clinical Modification
ILD	Interstitial lung disease
IPF	Idiopathic pulmonary fibrosis
IRB	Institutional Review Board
LDL	Low-density lipoprotein
OTC	Over-the-counter
PFT	Pulmonary function test
PS	Propensity score
PT	Prothrombin time
ROC	Receiver operating characteristic
SD	Standard deviation
SLB	Surgical lung biopsy
TLC	Total lung capacity

4. ABSTRACT

Name of company: Boehringer Ingelheim (BI)			
Name of finished medicinal product: Ofev (BI)			
Name of active ingredient: Nintedanib			
Protocol date: 18 December 2018	Study number:	Version/Revision: 1.0	Version/Revision date: 18 December 2018
Title of study:	Characteristics of IPF patients initiating nintedanib, pirfenidone or no antifibrotic treatment in the US		
Rationale and background:	
Idiopathic Pulmonary Fibrosis (IPF) is a debilitating, life limiting condition with a median survival range of 2.5 to 3.5 years from the time of diagnosis and an estimated incidence of 6.8-16.3 per 100,000 persons. Despite its rarity, the economic burden of IPF is significant, with the annual medical cost to the US healthcare system estimated at close to \$2 billion in 2012. The goals of treatment for IPF are to stop disease progression, reduce symptoms, prevent acute exacerbations, and prolong survival. The treatment options for IPF were limited until the FDA approved two products in October 2014, Ofev (nintedanib, BI) and Esbriet (pirfenidone, Genentech), that slowed disease progression. BI is interested in conducting research to understand differences in characteristics of patients who are prescribed these two drugs, and those who do not receive a prescription for an antifibrotic treatment.
		
Research question and objectives:	
To understand characteristics of patients treated with nintedanib and pirfenidone, as well as patients who do not receive a prescription for an antifibrotic treatment.
 
The primary objective is:
 
1. To describe and compare demographic, clinical, and other characteristics of IPF patients initiating nintedanib, pirfenidone, or not receiving prescription antifibrotic treatment 
The secondary objective is:
 
2. To compare and contrast the probability of receiving nintedanib vs. pirfenidone and nintedanib or pirfenidone vs. untreated in IPF patients using baseline patient characteristics		
Study design:	A retrospective cohort database study		
Population:	This study will use data from GE Centricity electronic medical records (EMR) database obtained from a national network of primary care practices in the US. The study population will include patients (\geq 40 years old) with \geq 1 diagnosis of IPF in EMR records and newly prescribed nintedanib or pirfenidone or patients with no prescription for		

	antifibrotic treatment between October 1, 2014 and April 30, 2018. Patients will be divided into three mutually exclusive cohorts: (1) nintedanib initiators; (2) pirfenidone initiators; and (3) control cohort who received no prescription antifibrotic treatment during selection window.										
Variables:	The following demographic and clinical characteristics as well as medical interventions for IPF during the 12-month baseline period (pre-treatment) will be evaluated and compared between cohorts 
 Demographic characteristics (e.g., age, gender, race/ethnicity, geographic region, insurance type) Clinical characteristics (e.g., selected comorbidities, baseline weight and body mass index [BMI], blood pressure, smoking status, laboratory measures, pulmonary function tests) Pharmacological interventions (e.g., index medication dose, time from the earliest diagnosis of IPF to index medication, other IPF treatments, bronchodilators, corticosteroids) Non-pharmacological interventions (e.g., surgical procedures, supportive therapies, diagnostic procedures) 										
Data sources:	GE Centricity EMR database from October 2013 to April 2018										
Study size:	A preliminary analysis identified 868 IPF patients with pirfenidone, 615 patients with nintedanib, and about 10,000 untreated patients.										
Data analysis:	Patient demographic and clinical characteristics will be described using descriptive analyses. Counts and percentages for categorical variables and measures of central tendency (mean, median, standard deviation [SD], and min/max) for continuous variables will be reported. Differences between the treatment cohorts (compared to each other and to untreated patients) will be assessed using absolute standardized differences and p-values. The probabilities of receiving one treatment over another will be tested by propensity scores and using multivariable logistic regression adjusted for key baseline characteristics. The similarities and differences between two treatment cohorts will be assessed using balance diagnostics tests. A stratified descriptive analysis will also be conducted at different time points to assess if the characteristics of the two exposures changes over time.										
Milestones:	
  
 Milestone	Planned Date	
   
 Start of data collection	December 2018 (start of data analysis)	
 
 End of data collection	March 2019 (end of data analysis)	
 
 Preliminary results	January/February 2019	
 
 Final report of study results	June 2019	
  
	Milestone	Planned Date	Start of data collection	December 2018 (start of data analysis)	End of data collection	March 2019 (end of data analysis)	Preliminary results	January/February 2019	Final report of study results	June 2019
Milestone	Planned Date										
Start of data collection	December 2018 (start of data analysis)										
End of data collection	March 2019 (end of data analysis)										
Preliminary results	January/February 2019										
Final report of study results	June 2019										

5. AMENDMENTS AND UPDATES

None

6. MILESTONES

Milestone	Planned Date
Start of data collection	December 2018 (start of data analysis)
End of data collection	March 2019 (end of data analysis)
Preliminary results	January/February 2019
Final report of study results	June 2019

7. RATIONALE AND BACKGROUND

Idiopathic Pulmonary Fibrosis (IPF) is a specific form of chronic, progressive fibrosing interstitial pneumonia of unknown cause, occurring primarily in older adults, and limited to the lungs.¹ IPF is a debilitating, life limiting condition with a median survival range of 2.5 to 3.5 years from the time of diagnosis.² A study using insurance claims data from the United States estimated the incidence of IPF to be between 6.8 and 16.3 per 100,000 persons.³ The same study yielded a prevalence estimate of between 14.0 and 42.7 per 100,000 persons, depending on the case definition used.³ The economic burden of IPF is significant, with the annual medical cost (hospitalization, emergency room [ER] visits, outpatient visits, and use of procedures and tests) to the US healthcare system estimated at close to \$2 billion in 2012.⁴

The goals of treatment for IPF are to stop disease progression, reduce symptoms, prevent acute exacerbations, and prolong survival.⁵ Pulmonary rehabilitation and oxygen treatment are commonly utilized as supportive treatments, and lung transplant surgery may be considered in some patients.⁵ Many pharmacological treatments (i.e. anticoagulants, combination of N-acetylcysteine, prednisone and azathioprine, selective endothelin receptor) have been evaluated in IPF patients; however, international guidelines recommend against the use of these treatments due to insufficient evidence.⁶ The treatment options for patients with IPF changed significantly in October 2014 when the FDA approved two products that slowed disease progression, Ofev (nintedanib, Boehringer Ingelheim) and Esbriet (pirfenidone, Genentech).^{7,8} Recently updated American Thoracic Society/European Respiratory Society/Japanese Respiratory Society, and Latin American Thoracic Association clinical practice guidelines gave conditional recommendations for the use of nintedanib and pirfenidone in the majority of patients with IPF.⁶

Several clinical trials have been conducted to evaluate the efficacy and safety of these two emerging treatments. A recent systematic review and meta-analysis of ten randomized controlled trials showed that both pirfenidone and nintedanib reduced the progression of IPF in terms of FVC (forced vital capacity) decline and had similar safety profiles.⁹ However, only nintedanib significantly reduced the risk of all-cause and respiratory death. Pirfenidone and nintedanib also reduced the risk of a $\geq 10\%$ decline in FVC over 12 months, although only nintedanib protected against the risk of acute exacerbations.⁹

Patients selected into clinical trials usually present with fewer comorbidities, fall between certain age limits, and the severity of their disease is defined.¹⁰ Therefore, clinical trial populations do not always reflect the entire population affected by IPF in the real-world setting. Understanding patient characteristics is essential when assessing the real-world effectiveness of a treatment. Unlike being randomly assigned to a treatment in clinical trials, patients in the real world may choose between similar treatments based on existing comorbidities and concomitant medications, differentiating the effectiveness of the medications in certain patients. When comparing nintedanib and pirfenidone, it is therefore important to understand the differences in clinical characteristics of patients who are prescribed nintedanib compared to patients who are prescribed pirfenidone, and how these patients compare to IPF patients who do not receive antifibrotic treatment.

In order to help identify the profile of patients and specific characteristics associated with initiating treatment for IPF, BI is conducting a retrospective database study to understand differences in characteristics of patients who are prescribed pirfenidone or nintedanib, and those who do not receive a prescription for an antifibrotic treatment. This study will also help identify patient characteristics driving the initiation of nintedanib or pirfenidone by assessing the probability of receiving the treatments.

8. RESEARCH QUESTION AND OBJECTIVES

The overall aim of this retrospective database study is to understand differences in characteristics of IPF patients who are prescribed nintedanib compared to those who are prescribed pirfenidone, and how these patients compare to patients who do not receive a prescription for antifibrotic treatment.

The primary objective is:

1. To describe and compare demographic, clinical, and other characteristics of IPF patients initiating nintedanib, pirfenidone, or not receiving prescription antifibrotic treatment

The secondary objective is:

2. To compare and contrast the probability (by propensity score) of receiving nintedanib vs. pirfenidone and nintedanib or pirfenidone vs. no treatment in IPF patients using baseline patient characteristics

9. RESEARCH METHODS

9.1 STUDY DESIGN

To address the objectives above, this retrospective database study will use a new user cohort design, where cohorts are defined based on the exposures of interest (i.e., prescription for nintedanib or pirfenidone or no antifibrotic treatment). The study population will consist of the following three mutually exclusive cohorts:

1. Nintedanib initiators, consisting of adult IPF patients who newly initiated nintedanib treatment
2. Pirfenidone initiators, consisting of adult IPF patients who newly initiated pirfenidone treatment
3. Untreated cohort, consisting of adult IPF patients without any prescription for antifibrotic treatment (i.e., no prescription for nintedanib nor pirfenidone)

The primary study endpoint is the absolute standardized differences (ASD) and p-value comparing patient characteristics between the two treatment cohorts and between each treatment cohort and the untreated cohort, where an ASD of at least 10% will be considered a meaningful difference. The secondary endpoint is the probability (estimated using propensity score) of receiving nintedanib vs. pirfenidone and that of receiving nintedanib or pirfenidone vs. no treatment based on patient characteristics; to identify baseline characteristics that drive initiation of a treatment while minimizing prescription bias.

These analyses will utilize real-world data to understand differences in patient characteristics between those prescribed nintedanib versus pirfenidone and those not receiving any antifibrotic treatments. The proposed data source, EMR data, allows exploration of several clinical characteristics (e.g., laboratory measures, medications, behavioral measures) in patients with IPF in a setting outside of a clinical trial.

9.2 SETTING

This retrospective database study will leverage the GE EMR data from October 1, 2013 to April 30, 2018. The EMR consists of patient data from ambulatory care records in the US and is representative of the US population receiving healthcare in the ambulatory setting. Patients will be included in one of three study cohorts based on prescription history from October 1, 2014 to April 30, 2018, allowing for a 12-month pre-index period to describe patient demographic, clinical and treatment characteristics.

Index date

The index date for the nintedanib (or pirfenidone) cohort will be the date of the first nintedanib (or pirfenidone) prescription during the selection window (from October 1, 2014 to April 30, 2018). The index date for the untreated cohort will be the date of the earliest IPF diagnosis or a randomly assigned date between October 1, 2013 and April 30, 2018.

Pre-index period

[figure not shown]
The pre-index period for each cohort will be the 12 months prior to the index date. Patients will be required to have ≥ 1 diagnosis of IPF during the pre-index period (see additional inclusion criteria described below).

Post-index period

The post-index period for each cohort will start from the index date. Since the study aims to evaluate patient characteristics during the pre-index period, no minimum follow-up will be required for post-index period and no study measures will be assess during the post-index period.

Patient selection is illustrated in Figure 1.

Figure 1. Patient Selection

Nintedanib cohort

Inclusion criteria:

- With ≥ 1 diagnosis for IPF (the International Classification of Diseases, Ninth Revision, Clinical Modification [ICD-9-CM] codes 516.3, 516.31, 515,¹¹ or ICD-10-CM codes J84.112) in the EMR between October 1, 2013 to April 30, 2018
- With ≥ 1 prescription for nintedanib between October 1, 2014 and April 30, 2018 (the selection window)
 - The date of the first prescription will be defined as the index date
- With ≥ 1 record in the EMR database during the 12 months prior to the index date (the pre-index period)
- With ≥ 1 diagnosis of IPF during the 12 months prior to the index date
- Age ≥ 40 on the index date
- will explore also requiring ≥ 1 chest CT scan before first IPF diagnosis during the pre-index period¹²

Exclusion criteria:

- With ≥ 1 diagnosis of other known causes of interstitial lung disease (ILD) on the date of or after the first IPF diagnosis during the pre-index period^{12,13}

- Other known causes of ILD include conditions such as systemic sclerosis, rheumatoid arthritis, systemic lupus erythematosus, dermatomyositis, polymyositis, Sjögren disease, and hypersensitivity pneumonitis (ICD-9-CM codes 135, 237.7, 272.7, 277.3, 277.8, 446.21, 446.4, 495, 500–505, 506.4, 508.1, 508.8, 516.0, 516.1, 516.32–516.37, 516.2, 516.8, 516.9, 517.0, 517.2, 517.8, 518.3, 555, 710.0, 710.0–710.4, 714.0, 714.81, 720, and 759.5, or ICD-10-CM equivalent codes)^{12,13}
- With ≥ 1 prescription for nintedanib prior to the index date
- With ≥ 1 prescription for pirfenidone prior to or on the index date

Pirfenidone cohort

Inclusion criteria:

- With ≥ 1 diagnosis for IPF (ICD-9-CM codes 516.3, 516.31, 515,¹¹ or ICD-10-CM codes J84.112) in the EMR between October 1, 2013 to April 30, 2018
- With ≥ 1 prescription for pirfenidone between October 1, 2014 and April 30, 2018 (the selection window)
 - The date of the first prescription will be defined as the index date
- With ≥ 1 record in the EMR database during the 12 months prior to the index date
- With ≥ 1 diagnosis of IPF during the 12 months prior to the index date
- Age ≥ 40 on the index date
- will explore also requiring ≥ 1 chest CT scan before first IPF diagnosis during the pre-index period¹²

Exclusion criteria:

- With ≥ 1 diagnosis of other known causes of interstitial lung disease (ILD) on the date of or after the first IPF diagnosis during the pre-index period^{12,13}
 - Other known causes of ILD include conditions such as systemic sclerosis, rheumatoid arthritis, systemic lupus erythematosus, dermatomyositis, polymyositis, Sjögren disease, and hypersensitivity pneumonitis (ICD-9-CM codes 135, 237.7, 272.7, 277.3, 277.8, 446.21, 446.4, 495, 500–505, 506.4, 508.1, 508.8, 516.0, 516.1, 516.32–516.37, 516.2, 516.8, 516.9, 517.0, 517.2, 517.8, 518.3, 555, 710.0, 710.0–710.4, 714.0, 714.81, 720, and 759.5, or ICD-10-CM equivalent codes)^{12,13}
- ≥ 1 prescription for pirfenidone prior to the index date
- ≥ 1 prescription for nintedanib prior to or on the index date

Untreated cohort

Inclusion criteria:

- With ≥ 1 diagnosis for IPF (ICD-9-CM codes 516.3, 516.31, 515,¹¹ or ICD-10-CM codes J84.112) in the EMR between October 1, 2013 to April 30, 2018
 - Index date will be defined as the date of the earliest IPF diagnosis or a randomly assigned date based on the exploratory analyses to be performed on the two treatment cohorts (exploring time from IPF diagnosis to treatment initiation)
 - will explore requiring ≥ 2 diagnoses for IPF that are ≥ 30 days apart to improve the identification of IPF patients^{12,13}
- With ≥ 1 record in the EMR database during the 12 months prior to the index date (the pre-index period)

- Age ≥ 40 on the index date
- will explore also requiring ≥ 1 chest CT scan before first IPF diagnosis during the pre-index period¹²

Exclusion criteria:

- With ≥ 1 diagnosis of other known causes of interstitial lung disease (ILD) on the date of or after the first IPF diagnosis during the pre-index period
 - Other known causes of ILD include conditions such as systemic sclerosis, rheumatoid arthritis, systemic lupus erythematosus, dermatomyositis, polymyositis, Sjögren disease, and hypersensitivity pneumonitis (ICD-9-CM codes 135, 237.7, 272.7, 277.3, 277.8, 446.21, 446.4, 495, 500–505, 506.4, 508.1, 508.8, 516.0, 516.1, 516.32–516.37, 516.2, 516.8, 516.9, 517.0, 517.2, 517.8, 518.3, 555, 710.0, 710.0–710.4, 714.0, 714.81, 720, and 759.5, or ICD-10-CM equivalent codes)^{12,13}
- With prescription for nintedanib or pirfenidone anytime during the data window

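### Untreated index dates may fall in the first data year, where the 12-month baseline set for every cohort cannot be observed

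*Combined protocol and SAP*

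**What the plan says.** All of the following is in the combined protocol and SAP.

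- **Data window (9.2).** "This retrospective database study will leverage the GE EMR data from October 1, 2013 to April 30, 2018".
- **Selection (9.2).** Patients enter one of the three cohorts on prescription history "from October 1, 2014 to April 30, 2018, allowing for a 12-month pre-index period". Treated index dates are first prescriptions inside that window.
- **Baseline (9.2, Pre-index period).** "The pre-index period for each cohort will be the 12 months prior to the index date".
- **Untreated index date (9.2, Index date).** "the date of the earliest IPF diagnosis or a randomly assigned date between October 1, 2013 and April 30, 2018".
- **Untreated index date again (9.2, Untreated cohort).** "Index date will be defined as the date of the earliest IPF diagnosis or a randomly assigned date based on the exploratory analyses" of time from diagnosis to treatment in the treated cohorts. No calendar floor is given, and the qualifying diagnosis may fall from October 1, 2013.
- **Minimum history (9.2).** Each cohort needs one EMR record in the 12 months before index.
- **Abstract, Population.** The third group is a "control cohort who received no prescription antifibrotic treatment during selection window".
- **Covariates (9.3.3).** Measures use the 12-month baseline. The index-year categories, for all cohorts, run from 2014 to 2018.

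**The concern.** The October 1, 2014 start exists so that a full year of data precedes each index date. The untreated index rule gives that up for one cohort only. An index in the first data year has a baseline cut off where the data begin, and one earlier record is enough to qualify.

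The loss falls on items that accumulate over the look-back: diagnosis, drug and procedure flags, and the liver and renal measures for which any abnormal history counts. Most other laboratory tests use the value nearest to index, so they mainly become missing and drop out of that comparison under 9.7.1. Age, sex, region, race and payer are not affected.

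Two of the three primary comparisons are exposed (nintedanib versus untreated and pirfenidone versus untreated), as is the treated-versus-untreated propensity model. Section 9.7.1 allows that model's covariates to be chosen on bivariate significance. Nintedanib versus pirfenidone is unaffected, because both cohorts are indexed from October 1, 2014. The effect has one direction: untreated patients look less ill and less investigated than they are. It inflates differences where treated patients have more history and hides them where untreated patients have more.

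**Working it through.** **1. Reproduce the plan's 12 months.** October 1, 2013 to October 1, 2014 is 365 days. The stated baseline therefore holds for every treated index date.

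**2. Apply the same dates to the untreated range.** October 1, 2013 to April 30, 2018 is 1,673 days. Index dates before October 1, 2014 occupy 365 of them, and 365/1,673 = 21.8%. Their look-back is 0 to 364 days, with a mean of 182 if uniform. Of these days, 92 fall in 2013, which has no index-year category. The other 365 - 92 = 273 fall in January to September 2014, which the category list would not catch.

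**3. Effect of the one-record rule.** Assume uniform index dates and Poisson records at v per year. With look-back L in years (capped at 1), a patient is kept with probability 1 - exp(-vL). The short share among those kept is 14% (v = 1), 18% (v = 4) and 20% (v = 12).

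**4. Spurious ASD.** Assume the same full-year prevalence p in both cohorts and two recording models:

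- *Single hazard:* every patient has hazard h = -ln(1 - p), so recorded prevalence at look-back L is 1 - exp(-hL).
- *Carriers:* a fraction c = p/(1 - exp(-4)) has the condition and is recorded an assumed 4 times a year, so recorded prevalence is c(1 - exp(-4L)).

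Average over index dates with the weights from step 3 to get the untreated prevalence q. Then use the protocol's formula, ASD = (p - q)/√{[p(1 - p) + q(1 - q)]/2}. Example: single hazard, p = 0.30, v = 12 gives q = 0.274 and ASD = 0.058.

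| p | Carriers, v = 1 / 4 / 12 | Single hazard, v = 1 / 4 / 12 |
|---|---|---|
| 20% | 0.008 / 0.013 / 0.019 | 0.024 / 0.035 / 0.046 |
| 30% | 0.010 / 0.017 / 0.025 | 0.030 / 0.045 / 0.058 |
| 50% | 0.016 / 0.025 / 0.038 | 0.042 / 0.062 / 0.082 |

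**5. Compare with the decision lines.** The plan calls an ASD of 0.10 meaningful. For p < 0.05, the protocol's standard error near d = 0 gives a threshold of 1.96 × √[(n1 + n2)/(n1 × n2)]. Section 9.5 gives 868 pirfenidone, 615 nintedanib and about 10,000 untreated patients, all preliminary:

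- pirfenidone versus untreated: 0.069
- nintedanib versus untreated: 0.081
- combined (868 + 615 = 1,483) versus untreated: 0.055

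Taking the artefact as roughly additive at p = 30% and v = 12, a true ASD of 0.10 - 0.025 = 0.075 (carriers) or 0.10 - 0.058 = 0.042 (single hazard) would already read as 0.10.

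**6. Precision after a floor.** Uniform dates leave 10,000 × 1,308/1,673 = 7,818 untreated. The 95% CI half-width goes from 0.081 to 0.082 (nintedanib) and from 0.069 to 0.070 (pirfenidone). With 5,000 left it would be 0.084 and 0.072.

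**The case against.** The best defence is that the 2013 date is a drafting slip. The selection sentence in 9.2 covers all three cohorts from October 1, 2014, the Abstract ties the controls to the selection window, and 9.3.3 has no 2013 index year. The untreated rule also awaits exploratory analyses, and Figure 1 is not shown. This may well be what was meant. But the index-date paragraph is explicit, the inclusion list sets no floor, and neither 9.9 nor 9.12 mentions unequal look-back. A programmer following 9.2 would implement the 2013 start.

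A second defence is that the artefact is small, and much of that stands. Chronic conditions and long-term drugs are recorded repeatedly, so the single-hazard figures run high for them. Both models also omit recording on the index date itself, which 9.3.3 counts for most measures though not for treatment history.

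A reader might infer that truncation alone will commonly exceed 0.10, pointing to the 76% with a pulmonary function test in 9.5. The documents do not support that. Under uniform dates, even the single-hazard model needs a prevalence of about 64% at 12 records a year, or 83% at 4. The 76% is no guide to flag prevalence: 1,150 of the 1,231 patients counted (93%) have an oxygen saturation value, and the plan analyses such results as value categories with missing values excluded. The nearest proxy for a spirometry flag is FEV/FVC, at 627/2,061 = 30% on the table's own nesting.

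**Conclusion.** The untreated index rule is wrong as written. It contradicts the 12-month baseline in the same section, and it disagrees with the Abstract and the index-year categories. This rests on dates alone and needs no modelling.

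The size cannot be fixed from the documents, because the distribution of untreated index dates is left open. Under uniform dates and 1 to 12 records a year, 14-20% of the untreated cohort has a short baseline. The spurious ASD at 20-50% prevalence is about 0.01-0.04 with carriers recorded 4 times a year, and 0.02-0.08 under the high-side single hazard. An earliest-diagnosis index could put more patients in the first data year, since people already ill may have their first code in the data early.

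The artefact will usually stay under 0.10 by itself. It matters because it is differential and one-directional, and because it can carry a modest true difference past 0.10 or past p < 0.05 in a study meant to find what distinguishes treated from untreated patients. It should be fixed before cohorts are built. A reader might infer that it undermines the whole study; it does not, since nintedanib versus pirfenidone is untouched.

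**What to change.** In Section 9.2, restrict untreated index dates, under either definition, to October 1, 2014 to April 30, 2018. Make the index-date paragraph and the untreated inclusion list say the same thing, in agreement with the Abstract and the index-year categories in 9.3.3. Exclude untreated patients whose index date falls before October 1, 2014 and report their number in the attrition table.

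The cost is a few sentences and some programming. Under uniform dates the untreated cohort falls from about 10,000 to about 7,800, which widens the ASD intervals by about 0.001. The real downside arises under an earliest-diagnosis index: untreated patients first diagnosed before the window are dropped, while treated patients with equally early diagnoses can stay. The reported exclusion count will show how much that matters.

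### If the untreated index is a random date, no rule requires the patient to be alive or in care on it, which can distort both comparisons with the untreated cohort

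*Combined protocol and SAP*

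**What the plan says.** Under Index date, section 9.2 sets the treated index at the first nintedanib or pirfenidone prescription. For untreated patients it gives two options: the earliest IPF diagnosis, "or a randomly assigned date between October 1, 2013 and April 30, 2018". The untreated inclusion criteria in the same section again offer the earliest diagnosis, but describe the random option differently, as "a randomly assigned date based on the exploratory analyses to be performed on the two treatment cohorts", meaning their times from diagnosis to treatment. The choice is left open.

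Untreated patients must have an IPF code in the data window, at least one record in the 12 months before index, age 40 or over at index, no other known cause of ILD, and no antifibrotic prescription in the data window. The general text on the pre-index period adds an IPF code in those 12 months for every cohort. On what follows the index date, the plan says "no minimum follow-up will be required for post-index period". Sections 9.9 (limitations) and 9.12 (bias) do not discuss whether an untreated patient is present at index.

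**The concern.** A prescription date shows that a treated patient was alive and in contact with care that day. A random date shows nothing of the kind. Take a patient with IPF coded in January 2016, a last record in March 2016 and an assigned index in November 2016. The patient meets the look-back rules, although nobody could have prescribed anything on the index date. The one criterion that looks past index, no antifibrotic in the data window, is met automatically by someone who has died or left.

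Treated patients therefore had to survive and stay in care until index, and untreated patients did not. A characteristic linked to early death or departure can separate the cohorts even if it plays no part in prescribing. This matters because section 9.1 aims to find the characteristics that drive initiation. Two of the three primary comparisons and the treated-versus-untreated propensity score use this cohort. Age at index, values taken closest to index, and the block on treatment on the index date are also unreliable for such patients.

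**Working it through.** The plan gives no figure on this point to reproduce. The check has three steps.

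**1. Closed form, deaths only.** Section 7 gives a "median survival range of 2.5 to 3.5 years" from diagnosis. Assume exponential survival with median m and rate λ = ln 2 / m.

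- Share dying within 12 months, 1 − 2^(−1/m): 24.2% for m = 2.5 years and 18.0% for m = 3.5 years.
- Mean share already dead at a date uniform over the 12 months after a single IPF code, 1 − (1 − e^(−λ))/λ: with λ = 0.277 this is 12.7%, and with λ = 0.198 it is 9.3%.

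If IPF is coded repeatedly, patients diagnosed longer ago also stay eligible, and the share rises.

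**2. Simulation with an index date and the 12-month look-back.** Assumptions:

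- IPF coded about quarterly while the patient is alive; deaths only.
- A 43-month window (October 1, 2014 to April 30, 2018).
- A constant treatment rate giving 12.9% treated. This uses section 9.5: (868 + 615) / (868 + 615 + 10,000) = 1,483 / 11,483.
- A marker with 40% prevalence, mortality hazard ratio 2 or 3, and no effect on treatment.
- Medians of 2.5 and 3.5 years, so four scenarios for each way of drawing the date.

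ASD is the section 9.7.1 formula for proportions.

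| Random date | Indexed after death | Marker ASD as written | Scenarios above 10% | ASD if presence at index is required |
|---|---|---|---|---|
| Uniform over the window | about 14–19% | about 5–12% | 1 of 4 | about 1–2% at most |
| Diagnosis plus treated delay | about 12–16% | about 7–16% | 2 of 4 | about 3–7% |

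Of about 10,000 untreated patients, 12–19% is roughly 1,200–1,900 if all were eligible. In the second row a residual remains because dropping patients who have gone shortens the untreated delays relative to the treated ones. Matching on time since diagnosis brings it down to about 1–2%.

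Sensitivity: if IPF is coded only once, at diagnosis, the treated-delay draw gives an ASD of 4.5–9.9%, and no scenario reaches 10%. The documents give no rate of leaving the database alive. At an assumed 0.2 per year, the share indexed after death or departure rises to as much as 29% (uniform date) or 21% (treated delays with an assumed mean of 0.5–1.0 year).

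**3. Cross-check by mixing.** Suppose 20% of the untreated cohort is indexed too late, and a characteristic has 20% prevalence in those still in care.

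- Odds tripled in the late group: prevalence there is 0.75/1.75 = 0.429. The mixture is 0.8 × 0.20 + 0.2 × 0.429 = 0.246. ASD = 0.046 / √[(0.160 + 0.185)/2] = 0.11.
- Odds doubled: the mixture is 0.227 and the ASD is 0.065.
- With 10% indexed late, doubling to quadrupling the odds gives 0.03–0.07.

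Only strongly linked characteristics reach the threshold through this artefact alone.

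**The case against.** The strongest reply is that the flaw belongs to one of two open options. If the earliest diagnosis is the index, the patient has a record that day and the problem does not arise. That stands, so the point is conditional. The random option is still live: the general text asks for an IPF code before index, which fits poorly with indexing on the first code unless the index day counts.

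The 12-month look-back also bounds the problem. A reader might infer that patients could be indexed years after death. They cannot: the last record must fall within the 12 months before index.

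A reader might also infer that the artefact usually exceeds 10%. Comparing ever-treated with never-treated patients at diagnosis, under the same marker assumptions, gives an ASD of 7.8–16.9%, above 10% in three of four scenarios. But that comparison contains neither the random date nor the look-back, so it measures survival to treatment in general, not this rule.

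Finally, it is tempting to say that sicker patients will always look untreated. After death or departure part of the baseline year is empty, so comorbidities, tests, oxygen and index-date drugs may be under-recorded. That can offset or reverse the excess. It is a second distortion from the same gap, not a defence, but it rules out a single stated direction.

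**Conclusion.** The point holds for the random-date option, on either description of the draw. As written, that option admits untreated patients who have died or left before index, and no section acknowledges it. About 12–19% of eligible untreated patients would be indexed after death, and a marker irrelevant to prescribing would show an ASD of about 5–12% or 7–16%, depending on the draw. These sizes rest on exponential survival, the assumed hazard ratios and prevalence, and quarterly coding; they are not estimates from the database. The 10% line can be crossed but need not be, and the net direction for a given variable is uncertain. The documents do not support extending the concern to the earliest-diagnosis option or to nintedanib versus pirfenidone. The plan should be changed before the cohort is built, because the bias enters at selection.

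**What to change.** In section 9.2, for the random option only, index each untreated patient on an actual EMR encounter, as the treated patients are:

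1. Set a target date: first IPF diagnosis plus a draw from the treated diagnosis-to-initiation times. Preferably, match each untreated patient to a treated patient and require the untreated patient to be still under observation at that time since diagnosis.
2. Take as index the first encounter on or after the target within a short window whose length is fixed in the protocol.
3. Exclude any patient with no such encounter, without re-drawing an earlier date, and report the number in the attrition table.

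Two shortcuts are not equivalent. Drawing the date between diagnosis and last record keeps early leavers and gives them an earlier index. Accepting a record at any time after the assigned date selects untreated patients on later survival.

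The cost is a short programming step, some loss from the roughly 10,000 untreated patients, where numbers are not limiting, and slight selection of frequent attenders, kept small by the short window. If the earliest diagnosis is chosen instead, none of this is needed.
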